	
will be stored for future testing of additional parameters in the research fields of acute decompensated heart failure and acute kidney injury.
 
Furthermore, the available laboratory values from routine clinical practice (see Table 1) will be entered in the Case Report Form (eCRF).
 
On days 1-5, the patient will be asked to complete a Patient Symptom Assessment Sheet (see Annex D).
 
On days 1 and 3, the treating physician will be asked to complete a very brief survey (Annex E) to provide a qualitative assessment of the patient's perceived intravascular volume status and renal function. The study physician will conduct a non-invasive clinical assessment of the patient (including e. g. body weight, height, edema grade, blood pressure, heart rate, respiratory rate, jugular venous distension assessment, oxygen saturation) on days 1-5.
 
In addition, the study physician will record in the eCRF detailed information regarding diuretics dosage, i. v. fluid application, and requirement of renal replacement therapy as ordered by the clinicians in the hospital.
 
Laboratory values and assessments (see Table 1) will be captured on each day that the VFI is administered and these data will be entered into the eCRF. Any AEs determined by the investigator to be related or possibly related to the VFI will be captured. Patients will also receive a follow up phone call 7 days (<math>\pm 2</math> days) after the second dose of VFI was administered, and a second follow up call 30 days after the second dose of VFI was administered. This second phone call will serve as the end-of-study (EOS) follow-up call. Any AEs determined by the investigator to be related or possibly related to the VFI will be captured during the follow up calls and will be followed to resolution. Additionally, in-person follow up visits may be scheduled, as determined by the investigator. During day 1-5, during follow-up phone calls or study visits and through information accessed within the hospital computer system or obtained from treating physicians or relatives, the following study outcomes will be recorded: mortality, length of hospital stay, readmission for heart failure, episodes of acute kidney injury, requirement of fluid resuscitation, episodes of symptomatic hypotension, successful reduction of body weight.
 
Upon conclusion of the study, the recorded clinical data will be provided to an independent data adjudication committee (DAC) in a pseudonymized fashion. The DAC will be asked to

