Laboratory values and assessments (see *Table 1*) will be captured on each day that the VFI is administered and these data will be entered into the CRF. Any AEs determined by the investigator will be captured. Patients will also receive a follow up phone call 7 days ( $\pm$  2 days) after the first dose of VFI was administered, and a second follow up call 30 days after the first dose of VFI was administered as an end-of-study (EOS) follow up call. Any AEs determined by the investigator will be captured during the follow up calls and will be followed to resolution. Additionally, in-person follow-up visits may be scheduled as needed.

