## 1.2 Trial design

This is an investigator-initiated, human clinical trial designed to evaluate the safety and functionality of the FAST PV and mGFR Technology in CHF patients.

Patients enrolled in the study will be administered VFI (Day 1) and with a second dose occurring 48h (+/- 5h) after the initial dose (Day 3).

After consenting to be enrolled in the study, patients meeting the enrollment criteria will receive a single dose of VFI. Blood draws (approximately 2 mL) will be collected pre-dose and at

---

15 ( $\pm 5$ ), 30 ( $\pm 5$ ), 60 (+30), and 180 (+120) minutes post-dose. The physician will remain present at the bedside of the patient for 10 minutes after administering the FAST VFI. Thereafter, the patient will be monitored on an ongoing basis, with clinical staff assessing the patient's condition along with the 15, 30, and 60 minutes blood draws specified in the protocol.

Patients will be treated according to standard of care throughout the time of their hospitalization. A second dose of VFI will be administered 48h (+/- 5h) after the initial dosing. Blood draws (approximately 2 mL) will be collected pre-dose and at 15 ( $\pm 5$ ), 30 ( $\pm 5$ ), 60 (+30), and 180 (+120) minutes post-dose.

Prior to administering the first and second dose of VFI, the physician will be asked to complete a very brief survey to provide a qualitative assessment of the patient's perceived volume status and renal function prior to initiating the FAST PV and mGFR measurements.

Laboratory values and assessments (see Table 1) will be captured on each day that the VFI is administered and these data will be entered into the case report form. Any AEs determined by the investigator will be captured. Patients will also receive a follow up phone call 7 days ( $\pm 2$  days) after the first dose of VFI was administered, and a second follow up call 30 days after the first dose of VFI was administered as an end-of-study follow up call. Any AEs determined by the investigator will be captured during the follow up calls and will be followed to resolution. Additionally, in-person follow-up visits may be scheduled as needed.

Table 1: Schedule of Study Events/Examinations

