#### 4.3.2 Safety/Tolerability

- Length of stay, dialysis/ultrafiltration requirement, or rehospitalization within 30 days, or mortality
- Laboratory values (Serum creatinine (mg/dl), Hematocrit (%), creatine phosphokinase (CPK) (U/l), NT-proBNP (ng/l), Alanine aminotransferase (ALT) (U/l), Aspartate aminotransferase (AST) (U/l), Alkaline phosphatase (AP) (U/l), bilirubin, total and direct (mg/dl), INR (dimensionless)) collected on day 1, 3, 5 (except for serum creatinine which is collected on all days and hematocrit which is only collected on day 1)
- Occurrence of AEs and SAEs
- Routine clinical parameters (Serum creatinine on admission (mg/dl), Baseline serum creatinine (nadir from inspection of previous, lab values or by primary care physician) (mg/dl), Serum creatinine (mg/dl), Serum sodium (mmol/l), Serum potassium (mmol/l), eGFR (CKD-EPI) (ml/min/1.73 m^2), Hemoglobin (g/dl), Serum-Albumin (g/dl), Urine output (0:00 - 24:00 on the indicated day) (ml/24 h) (if, incomplete, extrapolate the available time period to 24 hours), Chest X-ray: evidence of pulmonary congestion, Chest X-ray: evidence of pleural effusion, Chest X-ray: evidence of cardiomegaly, Alanine aminotransferase (ALT) (U/l), Aspartate aminotransferase (AST) (U/l), Alkaline phosphatase (AP) (U/l), Bilirubin, total and direct (mg/dl))

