## **5 Handling of missing values and outliers**

### **5.1 Missing values**

For the safety assessment of the AEs and SAEs, completeness of the data (severity, relationship, and seriousness) is required. The rate of missing values for the concentrations of FD003 is expected to be low. A decision on how to handle missing value for these values will be made during the data review (see section 6). Serum creatinine values missing at day 1 or 3 will be replaced by the respective values of day 0 and day 4 or the routine measurements at these days, if the aforementioned values are not available. For secondary parameters, missing values will not be replaced.

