To evaluate whether patients with a high mPVS ( $> +10\%$ ) or a high mTBVS ( $> +10\%$ ) on day 1 and/or day 3 are at risk of being refractory to diuretic therapy (defined as any dosage increases of furosemide i.v. dose equivalent, adding thiazide after day 1, require ultrafiltration/RRT within the next 24-48 hours, fail to improve subjectively in PGA and dyspnea scales, fail of mean weight loss during the study period Day 1-Day 5 of at least 0,5 kg/d) logistic regression models using mPV and mTBV as independent variables will be used.

To evaluate whether the changes of ePV (using relative and absolute change as well as the Strauss' formula) and eTBV (using relative and absolute change) from day 1 to day 3 adequately reflects the changes of mPV and mTBV Bland-Altman plots will be generated. These plots will be analysed exploratory, since no appropriate values for limits of agreements are available. The amount of values within 10% and within 30% of the measured values will also be determined. In addition, the diagnostic test accuracy including 95% confidence interval as proposed by Obuchowski will be calculated.

To evaluate whether the change of mPV and mTBV and changes of mPVS and mTBVS from day 1 to day 3 as well as the mPVS and mTBVS on Day 1 and Day 3 is predictive of the remaining length of stay at the given day (i.e. remaining length of stay starting with day 1 or with day 3), dialysis/ultrafiltration requirement, or rehospitalization within 30 days, or mortality, linear (remaining length of stay), logistic (dialysis/ultrafiltration, rehospitalization within 30 days) or Cox-regression models (mortality) will be utilized using changes of mPV and mTBV from day 1 to day 3 (first model), changes of mPVS and mTBVS from day 1 to day 3 (second model), and mPVS and mTBVS at day 1 (third model) and day 3 (fourth model) as independent variables.

To evaluate whether the percentage changes of mGFR from day 1 to day 3 ( $< 0$  vs.  $\geq 0$ ; continuous) predicts the percentage changes of eGFR from day 2 to day 4 (CKD-EPI formula only;  $< 0$  vs.  $\geq 0$ ; continuous), a logistic as well as a linear regression model will be used.

The same will be done to investigate the changes in eGFR from day 1 to day 3 (all formulas) as the dependent variable. Further, exploratory Bland-Altman plots without predefined limits of agreement will be created.

To evaluate whether patients with a high PVS or TBVS on Day 1 ( $> +10\%$ ) and a decreasing PVS

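### The start of 30-day rehospitalisation is undefined, and the planned logistic model takes no account of time at risk, which shortens as the hospital stay lengthens

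*SAP*

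**What the plan says.** SAP 7.7.1 takes changes in measured plasma and blood volume from Day 1 to Day 3, and volume status on each of those days, as predictors of several outcomes. Remaining length of stay gets a linear model; for the others, "logistic (dialysis/ultrafiltration, rehospitalization within 30 days) or Cox-regression models (mortality) will be utilized". The independent variables are volume terms only. There is no offset, no censoring for rehospitalisation and no term for day of discharge.

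The same sentence gives remaining stay an explicit start: "remaining length of stay starting with day 1 or with day 3". Rehospitalisation gets none. SAP 4.3.2 lists it as "Length of stay, dialysis/ultrafiltration requirement, or rehospitalization within 30 days, or mortality", and Protocol 4.2 and 14 and SAP 1.1 are equally silent. SAP 8 (Changes from the protocol) does not take it up.

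The cause is also open. The Study design part of the protocol synopsis records "mortality, length of hospital stay, readmission for heart failure", whereas the SAP names no cause.

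The last contact is described in different ways:
- Protocol synopsis: "a second follow up call 30 days after the second dose of VFI was administered".
- Protocol 4.4: "a second follow up call 30 days after the first dose of VFI was administered as an end-of-study (EOS) follow up call".
- SAP 1.2: "a second follow up call 30 days after the first dose of VFI was administered as an end-of-study follow up call".
- Table 1 in both documents: a column headed Day 30.

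On incomplete data, SAP 5.1 says: "For secondary parameters, missing values will not be replaced".

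**The concern.** Every patient is in hospital at inclusion (Protocol 5.1), and Table 1 places the Day 5 assessments before discharge. Nobody can be readmitted until discharged, so the calendar between discharge and the end of observation is the time at risk.

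A logistic model of a yes/no outcome treats all patients as equally exposed. Here they are not, and what makes exposure unequal (length of stay) is itself modelled on the same volume terms. If volume is related to stay, which is what the SAP sets out to examine, the rehospitalisation odds ratio could differ from 1 with no effect of volume on readmission. The reported frequency would also depend on a window that the reader cannot identify. SAP 7.1 says the results are meant to generate hypotheses for phase III, so such an association could be carried forward.

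**Working it through.** **Final contact.** Dose 1 is on Day 1 and dose 2 on Day 3. The second-dose anchor gives 3 + 30 = Day 33, which reproduces the 33-day patient duration in the synopsis timetable. The first-dose anchor gives 1 + 30 = Day 31. Table 1 gives Day 30.

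**Days at risk** = end day F minus discharge day D.

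| End day F | D = 5 | D = 10 | D = 15 |
|---|---|---|---|
| 30 (Table 1) | 25 | 20 | 15 |
| 31 (Protocol 4.4, SAP 1.2) | 26 | 21 | 16 |
| 33 (synopsis) | 28 | 23 | 18 |

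The table serves both readings. A window opening on Day 1 or Day 3 closes on Day 31 or Day 33. A window opening at discharge but observed only to the last scheduled contact ends on the same days. It is complete only if D ≤ F − 30, that is Day 0, 1 or 3. At the upper limit of the 30 ± 5 days in Protocol 7.5 (Day 36), it is complete for discharge by Day 6.

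**Illustrative size.** The documents give no readmission rate. Assume a 30-day post-discharge risk p = 0.20 (range 0.10 to 0.30), a constant hazard and no effect of volume.

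- Hazard h = −ln(1 − p)/30 = 0.2231/30 = 0.00744 per day.
- Observed risk = 1 − exp(−h(F − D)). With F = 31: D = 5 gives 17.6%, D = 10 gives 14.5%, D = 15 gives 11.2%.
- Odds ratio, D = 15 against D = 5: (0.112/0.888)/(0.176/0.824) = 0.59. Over p of 0.10 to 0.30 and F of 30 to 33 the range is 0.56 to 0.63.
- Hazard shape matters. With p = 0.20, F = 31 and a Weibull hazard of shape 0.6 (declining), the same contrast is 0.73.

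**Per SD of a volume predictor.** This was simulated in 400,000 patients with no true effect, p = 0.20, F = 31, constant hazard, log-normal remaining stay (sigma 0.5), earliest discharge Day 5, and a predictor correlated r with log stay. All of these inputs are assumptions.

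| Median remaining stay (days) | r | Null OR per SD | Log OR |
|---|---|---|---|
| 6 | 0.3 | 0.959 | −0.04 |
| 9 | 0.5 | 0.876 | −0.13 |
| 12 | 0.5 | 0.817 | −0.20 |

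Under the declining hazard these become about 0.97, 0.91 and 0.86.

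**Against sampling error.** At n = 50 and an observed rate of 14.5%, the standard error of the log OR per SD for a single predictor is 1/√(50 × 0.145 × 0.855) = 0.40. The constant-hazard bias is therefore about 0.1 to 0.5 of one standard error. SAP 7.7.1 names a plasma and a blood volume term in each model, and SAP 7.2 derives measured blood volume from measured plasma volume. The two are collinear, so the real standard error is larger.

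**The case against.** The best defence is that the documents do imply a window. An exclusion criterion (Protocol 5.2) speaks of the 30 days during which patients are enrolled, and Protocol 7.5 gives about 30 days from enrolment. Rehospitalisation would then simply mean readmission during study follow-up. This is a reasonable reading, but it is exactly the one in which time at risk falls day for day with stay, so it does not rescue the logistic model.

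It does dispose of one tempting inference. A reader might conclude that the planned call dates lose events: if all 50 patients left on Day 10, about 7 readmissions would be seen by Day 31 instead of 10. The comparison figure of 10 belongs to a 30-day window from discharge, which the documents never claim, so no event is shown to be lost.

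The defence also notes that the synopsis allows outcomes to be taken from the hospital computer system, treating physicians or relatives, and that an unplanned readmission would generally be an SAE. That stands: capture need not stop at the call. But no end date is set for the search, so equal exposure is still not assured.

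Finally, all analyses are declared descriptive (SAP 7.1), the bias is small against sampling error, and the data review meeting (SAP 6) may document additions to the analysis. All three points stand. They limit the importance of the concern and offer a route for correcting it, but they do not supply the missing definition.

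**Conclusion.** The concern holds in a limited form. The start of the window and the cause of readmission are not stated. On an enrolment-anchored window, or a discharge-anchored one restricted to scheduled contacts, the logistic odds ratio can mix readmission risk with exposure time. The likely distortion is small at 50 patients (null OR per SD of about 0.96 to 0.82 under a constant hazard, against a standard error of about 0.40). It rests on assumed readmission risk, hazard shape, stay distribution and correlation. It touches one exploratory secondary outcome; the primary endpoints and safety counts are unaffected.

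Two further inferences are not supported:
- A reader might infer that high volume would look protective. That requires high volume to lengthen the stay. Neither document says so, and two of the four models use change in volume. The direction is unknown.
- A reader might infer that timing from discharge makes the Day 30/31/33 discrepancy irrelevant. It does not: the contact date would still set the number of events, the precision and the length of follow-up observed.

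**What to change.** Before analysis, in the SAP or the data review report:

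1. State whether rehospitalisation means heart failure or any cause.
2. Start the clock at discharge from the index stay.
3. Analyse time from discharge to first readmission by Cox regression (cause-specific hazard), censored at death, last contact or 30 days after discharge, whichever comes first. Cox regression is already planned for mortality in the same sentence.
4. Report in-hospital deaths separately, since these patients are never at risk.
5. Report readmission as observed during study follow-up, together with the distribution of days at risk.

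The cost is a few lines of text and one derived time, with no new patient contact. The discharge date is already needed for length of stay. The limits should be stated too. Events will be few. Protocol Tables 2 to 9 list no readmission date, so it must come from SAE or hospital records, and an SAE onset date need not equal the admission date. On the three stated call dates, scheduled contacts alone cannot give full 30-day post-discharge incidence for patients discharged on Day 5 or later.

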### **Size Estimation**

We plan to enrol 50 eligible patients. Due to the explorative nature of this phase II study a formal sample size calculation is not possible. However, the sample size of 50 patients is sufficient to guarantee reasonable accuracy with respect to the main objectives of the trial as specified below.

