### Sample size

The primary objective is to assess the safety and function of the FAST PV and mGFR Technology in hospitalized patients with heart failure. This is a phase II trial. It is planned to enroll 50 eligible patients. No formal hypothesis test is performed to assess the primary objective. This is justified as follows:

1. Both function and safety cannot be uniquely assessed by one specific endpoint, but there exist several relevant endpoints and endpoint-related criteria which must be investigated in order to assess the global function and safety.
2. For reasons of feasibility, the studies sample size is limited to 50 patients which is an adequate number in the context of a phase II trial. However, this limited number does not allow to address a complex multiple testing problem with adequate power.

Therefore, all analyses are purely descriptive.

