### 4.3 Secondary variables

#### 4.3.1 Efficacy

- Estimated PV (by Kaplan-Hakim's formula, see chapter 7.2) and measured PV (assessed by FAST methodology) on days 1 and 3
- Estimated TBV (by Nadler's formula, see chapter 7.2) and measured TBV (mTBV: calculated from mPV and measured hematocrit, see chapter 7.2) on days 1 and 3
- Estimated GFR (CKD-EPI formula, sMDRD, Cystatin C formula, and Creatinine-Cystatin C formula, see chapter 7.2) and measured GFR (assessed by FAST methodology) on days 1 and 3 in heart failure patients undergoing active fluid management
- Development of AKI within 72 hours after day 1 and 48 hours after day 3 respectively
- Current level and level within last 24 hours of well-being, dyspnea, dizziness, nausea reported on day 1 and day 3
- Subjectively reported symptoms (PGA, dyspnea, dizziness, nausea) determined using patient symptom assessment sheets within the following 24 and 48 hours on day 1 and following 24 and 48 hours on day 3
- Low-output complications within the next 24 and 48 hours (e. g. subjectively reported dizziness/nausea, PGA, hypotension (Systolic <100, diastolic <60mmHg), need for iv-fluid therapy) at day 1 and within the next 24 and 48 hours at day 3
- Risk of being refractory to diuretic therapy (e. g. require dosage increases of furosemide/torsemide, require ultrafiltration/RRT within the next 24-48 hours, fail to improve subjectively in PGA and dyspnea scales) within 24 and 48 hours on day 1 and day 3

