## 7.2 Derived Parameters

The following formulas will be used for determination of estimated and measured TBV, ideal TBV, estimated and measured total blood volume status (eTBVS and mTBVS), ePV, estimated PV change, ideal PV, estimated and measured plasma volume status (ePVS and mPVS), and eGFR on day 1 and day 3:

Nadler formula for eTBV (Sharma & Sharma, 2020):

- Men:  $eTBV [L] = (0.3669 \times \text{Height [m]}^3) + (0.03219 \times \text{Weight [kg]}) + 0.6041$
- Women:  $eTBV [L] = (0.3561 \times \text{Height [m]}^3) + (0.03308 \times \text{Weight [kg]}) + 0.1833$

mTBV will be calculated as follows:

- $mTBV [mL] = mPV [mL] / (1 - \text{hematocrit [\%]} / 100)$

Lemmens-Bernstein-Brodsky formula for ideal TBV (iTBV) (Lemmens, Bernstein, & Brodsky, 2006):

- $iTBV [mL/kg] = 70 / [\text{sqrt}(\text{body mass index}/22)]$  – the lowest body weight during the days 1 to 5 will be used for calculation of BMI
- $iTBV [mL] = iTBV [ml/kg] \times \text{weight [kg]}$  – the lowest body weight during the days 1 to 5 will be used for calculation

Estimated and measured total blood volume status:

- $eTBVS [\%] = \text{Percentage change from iTBV: } (eTBV - iTBV) / iTBV$
- $mTBVS [\%] = \text{Percentage change from iTBV: } (mTBV - iTBV) / iTBV$

Kaplan-Hakim Formula for ePV (Ling et al., 2015):

- Men:  $ePV [mL] = (1 - \text{hematocrit [\%]}) \times [1530 + (41 \times \text{weight [kg]})]$
- Women:  $ePV [mL] = (1 - \text{hematocrit [\%]}) \times [864 + (47.9 \times \text{weight [kg]})]$

Strauss formula for plasma volume change (Strauss, Davis, Rosenbaum, & Rossmeis, 1951):

- $PV\_2/PV\_1 \times 100 [\%] = \text{hemoglobin\_1 [g/dL]} / \text{hemoglobin\_2 [g/dL]} \times (1 - \text{hematocrit\_2 [\%]}) / (1 - \text{hematocrit\_1 [\%]}) \times 100$

Plasma volume change will also be calculated via the ratios of ePV by the Kaplan-Hakim-Formula

Harrison formula for ideal PV (iPV) (from Ling 2015):

- Men: iPV [mL] = 39 [mL/kg] × weight [kg] – the lowest body weight during the days 1 to 5 will be used for calculation
- Women: iPV [mL] = 40 [mL/kg] × weight [kg] – the lowest body weight during the days 1 to 5 will be used for calculation

Estimated and measured plasma volume status (ePVS and mPVS):

- ePVS [%] = Percentage change from iPV: (ePV - iPV)/iPV
- mPVS [%] = Percentage change from iPV: (mPV - iPV)/iPV

The eGFR will be calculated using CKD-EPI formula (Levey et al., 2009):

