### 7.7 Secondary analyses

#### 7.7.1 Efficacy

To evaluate how estimated PV (ePV) and estimated total blood volume (eTBV) assessments on days 1 and 3 (by Nadler's formula, Kaplan-Hakim formula) predict measured PV (mPV; as assessed by FAST methodology) and measured TBV (mTBV; calculated from mPV and measured hematocrit) at these time points, linear regression models with the measured values at a given day as dependent variable and the estimated version as independent variable will be generated. The models will be adjusted for BMI, weight, and height separately.

Further, Bland-Altman plots will be generated comparing the estimated and measured parameters separately for day 1 and day 3. The defined limits of agreement are  $\pm 500\text{ml}$  for TBV and  $\pm 300\text{ml}$  and for PV. The amount of values within 15% and within 30% of the measured values will also be determined. In addition, the diagnostic test accuracy including 95% confidence interval as proposed by Obuchowski (Obuchowski, 2005) will be calculated. The interpretation for a continuous reference standard is as follows: Of two randomly chosen patients, the diagnostic accuracy is the probability that the patient with the higher reference standard result has a higher diagnostic test result than the patient with the lower reference standard test result. In the case of the study, the measured PV and TBV will act as reference standard while the estimated versions serve the diagnostic test.

To evaluate how a clinical evaluation on days 1 and 3 predicts mPV and mTBV at these time points, linear regression models will be used.

Depending on the amount of available information and distribution, the following parameters will be considered for the analysis in the order of appearance: hematocrit (only PV), mean arterial blood pressure, BMI (only PV), weight, height (BMI, weight, height will be entered in 3 separate models), age, gender, NYHA stage, respiratory rate, edema grade, presence of pulmonary rales, jugular venous congestion. At least 10 observations will be needed per parameter that need to be estimated. Bland-Altman plots, frequencies within 15% and 30%, and diagnostic accuracy will be evaluated as stated before.

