To evaluate whether eGFR calculation by the CKD-EPI formula and sMDRD formula on days 1 and 3 provides an accurate estimate of measured GFR (mGFR; assessed by FAST methodology) in heart failure patients undergoing active fluid management, linear regression models with the measured value at a given day as dependent variable and the estimated version as independent variable will be generated. The models will be adjusted for mPV and mPVS. Further, Bland-Altman plots will be generated comparing the estimated and measured parameters separately for day 1 and day 3. The defined limits of agreements are  $\pm 6\text{ml/min}$ . Diagnostic accuracy including frequencies of values between 15% and 30% of the measured value will be determined as mentioned before.

To evaluate whether patients with a low mGFR/eGFR ratio on days 1 and 3 are at higher risk of developing AKI within the following 72 (day 1) and 48 (day 3) hours, logistic regression models with the AKI status as dependent variable and mGFR/eGFR ratio as independent variables will be generated. The models will be adjusted for mPVS, mTBVS. Three different versions of the mGFR/eGRF ratio will be evaluated: ratio  $< 1$ ; ratio  $<$  first quartile; ratio as continuous parameter.

To evaluate whether ranges of mPVS (low mPVS ( $< -10\%$ ), normal mPVS ( $-10$  to  $+10\%$ ), high mPVS ( $> +10\%$ )) and/or mTBVS (low mTBVS ( $< -10\%$ ), normal mTBVS ( $-10$  to  $+10\%$ ), high mTBVS ( $> +10\%$ )) on days 1 and 3 are associated with subjectively reported symptoms (current PGA  $> 15$ , current dyspnea  $> 15$ , current dizziness  $> 15$ , current nausea  $> 15$ ) determined using patient symptom assessment sheets within the following 24-48 hours, a logistic regression

---

model with occurrence of symptoms (PGA, dyspnea, dizziness, nausea) as dependent variable and the categorized measured value (mPVS, mTBVS) as independent variables will be generated. The models will be adjusted for mean arterial pressure.

To evaluate whether patients with low mPVS ( $< -10\%$ ) or low mTBVS ( $< -10\%$ ) on day 1 or on day 3 are at risk of developing low-output complications within the next 24-48 hours (subjectively reported dizziness  $> 15$ , nausea  $> 15$ , PGA  $< 25$ , hypotension (Systolic  $< 100$ , diastolic  $< 60$  mmHg), need for iv-fluid therapy), logistic regression models using mPVS and mTBVS as independent variables will be used.

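### Four outcome models each appear to carry a PV term and a TBV term, although TBV is computed from PV: the separate coefficients will be unstable, most of all for changes, and the logistic and Cox models have no event limit

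*SAP*

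**What the plan says.** SAP 7.7.1 plans linear regression for remaining stay, logistic regression for dialysis or ultrafiltration and for 30-day readmission, and Cox regression for death. The predictors come in four numbered sets. The first is "changes of mPV and mTBV from day 1 to day 3 (first model". The second holds the changes of the two status variables. The list ends "and mPVS and mTBVS at day 1 (third model) and day 3 (fourth model) as independent variables".

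The TBV term is not measured independently. SAP 4.3.1 describes it as "calculated from mPV and measured hematocrit, see chapter 7.2", and SAP 7.2, after "mTBV will be calculated as follows", gives mTBV = mPV/(1 - hematocrit/100).

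The same pair appears elsewhere in SAP 7.7.1. The low-output models use mPVS and mTBVS, and the diuretic-refractory models use mPV and mTBV. For the AKI models the SAP says "The models will be adjusted for mPVS, mTBVS".

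The one rule on model size is "At least 10 observations will be needed per parameter that need to be estimated". It sits in the paragraph on the clinical-evaluation linear models. SAP section 8 drops variable selection, so no stated step would remove a redundant term. On size, the SAP says "It is planned to enroll 50 eligible patients", and the protocol's Size Estimation says that "a formal sample size calculation is not possible".

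**The concern.** TBV is PV plus red-cell volume. If red-cell volume hardly moves in 48 hours, the true TBV change equals the true PV change. The TBV coefficient given PV then mostly reflects hematocrit error. A real association would be divided between two near-copies with inflated standard errors and possibly opposite signs. The report could then call volume change not predictive, or describe a contrast between PV and TBV that does not exist.

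The second part is sparse events. In logistic and Cox models precision depends on events rather than patients, and the SAP sets no minimum. The general remarks in SAP 7.1 say the results are meant to generate hypotheses for phase III, and a coefficient whose sign is close to arbitrary would mislead that step.

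**Working it through.** The plan has no calculation to reproduce: 50 is a feasibility figure, and no event rate or power is stated for these models.

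**1. Joint or separate entry.** Each of the four sets names two terms as independent variables. Single-term fits would need eight sets. Where the SAP wants separate models it says so: BMI, weight and height go into three separate clinical-evaluation models. Joint entry is therefore the natural reading, though the word is not written.

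**2. Collinearity of the changes (first model).** All numerical inputs are assumptions: mean PV 3.5 L, mean hematocrit 37%, constant red-cell volume, PV change SD 7 to 12%, hematocrit error SD 0.5 to 2 points.

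- TBV = 3.5/0.63 = 5.56 L.
- An error d in hematocrit (as a fraction) shifts mTBV by about TBV/(1 - Hct) x d = 8.82 x d litres.
- The error SD of the change over two days is 8.82 x d x √2: 0.0624 L for 0.5 points, 0.125 L for 1 point, 0.249 L for 2 points.
- The SD of PV change is 0.07 x 3.5 = 0.245 L or 0.12 x 3.5 = 0.42 L.
- With true changes equal, VIF = 1/(1 - r²) = 1 + (SD of PV change / SD of error)².

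| Hct error | PV change SD 7% | PV change SD 12% |
|---|---|---|
| 0.5 points | 16 | 46 |
| 1 point | 4.9 | 12 |
| 2 points | 2.0 | 3.8 |

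Simulation from the SAP formula, with PV measurement error of 0 to 3% added, gives about 5 to 44 for errors of 0.5 to 1 point across the two change models, and 2 to 4 for 2 points. The fall at 2 points is no comfort, because the TBV term is then largely noise. Standard errors grow by √VIF: √5 = 2.2 to √44 = 6.6 fold. Over a wider grid of inputs the VIF runs from about 1.5 to 43. If hematocrit instead varies independently of PV (SD 1 to 4 points), it is 3.5 to 32.

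**3. If hematocrit exists on day 1 only.** SAP 4.3.2 says so. The protocol (synopsis and Table 7) says days 1 and 3. With a single hematocrit, mTBV change = mPV change/(1 - Hct), percentage changes in PV and TBV are identical, and the VIF exceeds 100 (about 60 to 355 over the wider grid).

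**4. Status models (third and fourth).** mPVS and mTBVS are scaled by different ideal volumes, which weakens the link: r = 0.76 to 0.93, VIF about 2 to 7, standard errors √2 = 1.4 to √7 = 2.6 fold. Raw mPV and mTBV levels, as listed for the diuretic-refractory models, give VIF 3 to 28.

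**5. Events.** Two slopes at 10 events each need 20 events, or 20/50 = 40%. One slope needs 10, or 20%. The rule on observations would allow 50/10 = 5 parameters whatever the number of events.

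| Assumed rate | Expected events | Per slope (two slopes) | P(at least 20) | P(none) |
|---|---|---|---|---|
| 2% | 1 | 0.5 | <0.001 | 0.36 |
| 5% | 2.5 | 1.25 | <0.001 | 0.08 |
| 20% | 10 | 5 | <0.001 | <0.001 |
| 30% | 15 | 7.5 | 0.085 | <0.001 |
| 40% | 20 | 10 | 0.55 | <0.001 |

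**6. Effect on estimates.** Logistic simulation: n = 50, odds ratio 2 per SD of PV, no separate TBV effect, r = 0.90 to 0.95, 400 runs per setting.

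| Event rate | Median SE, PV alone | Median SE, both | Wrong sign, PV alone | Wrong sign, both |
|---|---|---|---|---|
| 5% | 0.69 | 1.55 to 2.27 | 13% | 30 to 35% |
| 10% | about 0.5 | 1.18 to 1.62 | 4 to 7% | 27 to 34% |
| 20% | 0.40 | 0.90 to 1.25 | 2 to 3% | 15 to 28% |

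Some simulated datasets showed separation, so the low-rate figures are indicative.

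**The case against.** Joint entry is inferred. Each numbered set serves four outcomes and three model types, so the numbers may label predictor lists rather than single fits. That stands as a reason to ask for clarification, and one sentence in the SAP would settle it.

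The question posed is whether volume predicts outcome, and collinearity does not spoil the joint prediction. This also stands: the harm is to the separate coefficients.

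A reader might infer that neither coefficient can be interpreted in any of the models. The documents do not support that. In the status models, TBV given PV has a meaning, roughly red-cell volume, and the inflation is moderate. The linear model for remaining stay uses all evaluable patients, so the event argument does not reach it. A reader might also infer that the AKI analysis suffers the same collinearity. There mPVS and mTBVS are only adjusters of the mGFR/eGFR ratio, and their mutual correlation does not in itself inflate the ratio's standard error. The redundant adjuster costs a parameter: three slopes at 10 events each would need 30 events, two would need 20.

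Finally, these are secondary analyses, which SAP 7.1 calls descriptive, p values included, and SAP section 8 acknowledges the limited sample. That limits the consequence but does not stabilise the estimates.

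**Conclusion.** The point holds in a limited form. Fitted as most naturally read, the plan gives unstable separate PV and TBV coefficients. In the two change models they are close to unidentifiable: VIF about 5 to 44, about 2 to 4 if hematocrit error is as large as 2 points, and above 100 if only a day 1 hematocrit exists. In the status models they are imprecise (VIF about 2 to 7) but not uninterpretable. The logistic and Cox models have no event limit, and 10 events for each of two slopes would be expected only at event rates of 40% or more.

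The algebraic link between mTBV and mPV is in the SAP. The VIFs rest on assumed variability and measurement error. For the change models they also rest on constant red-cell volume, which is plausible over 48 hours because active internal bleeding is an exclusion criterion. Event rates are not in the documents, so the size of the shortfall is conditional on them. The change should be made before analysis, but it does not affect the primary objective.

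**What to change.** - **One volume measure per model.** In the outcome models of SAP 7.7.1, fit mPV change, mTBV change, mPVS and mTBVS (changes and day values) each alone. Do the same in the low-output and diuretic-refractory models.
- **AKI models.** Keep one of mPVS or mTBVS, to save a parameter and not because of collinearity with the ratio.
- **Events.** For logistic and Cox models, apply the 10-per-parameter rule to events. With fewer than 10 events, report them descriptively with their predictor values, or give at most one single-predictor penalised (Firth) estimate labelled exploratory.
- **Hematocrit days.** Reconcile SAP 4.3.2 (day 1 only) with the protocol synopsis and Table 7 (days 1 and 3). SAP 7.2 itself needs a second value for day 3 mTBV and for the Strauss formula.

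The cost is SAP wording, with no new data. Predictor sets rise from four to eight, so fits across the four outcomes rise from 4 x 4 = 16 to 8 x 4 = 32, each simpler. The joint PV/TBV contrast is given up.
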